7 STUDY DESIGN

7.1 Overall Study Design and Investigational Plan

This is a Phase IIa open-label, multicenter safety and efficacy study of MOR00208, that will enrol approximately 40 to 120 adult patients with refractory or relapsed NHL who have received at least 1 prior therapy containing rituximab.

The study will enrol patients from four different NHL subtypes: FL, DLBCL, MCL and other indolent NHL (MZL, MALT, etc.).

The study will employ a two-stage design where the decision to further enrol any NHL subtype in Stage 2 will depend on best responses after 2 or 3 cycles in Stage 1.

Stage 1 – At least ten patients per NHL subtype (a minimum of 40 patients in total) will be enrolled to receive MOR00208 12 mg/kg weekly for 8 weeks. After 8 and 12 weeks (the latter applicable only for patients with at least SD after 8 weeks) of dosing, patients will be evaluated for response. If in Stage 1 fewer than 2 patients per NHL subtype have a best response of PR or better, then continued enrolment in that cohort will be stopped for futility. If at least 2 patients per NHL subtype have a best response of PR or better, then additional patients will be enrolled into Stage 2 for that subtype cohort.

Any patients with a response of at least stable disease (SD) in Stage 1 will qualify for a further 4 weeks of dosing.

Stage 2 – At least an additional 20 patients will be enrolled for each NHL cohort demonstrating a response in Stage 1. After 8 weeks, the ORR will be evaluated for each NHL cohort.

Any patients with a response of at least stable disease (SD) in Stage 2 will qualify for a further 4 weeks of dosing.

Maintenance treatment - Patients with an ongoing response of at least PR at the end of Cycle 3 (regardless of Stage 1 or 2) may receive further study drug until progression (please see Sections 10.3 and 10.4). Eligible patients will receive a dose of 12 mg/kg MOR00208 either monthly or every second week.

The decision on patient eligibility and dosing frequency for this maintenance treatment will be taken jointly on a case-by-case base by the concerned investigator and the sponsor.

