2.2.2 Secondary Endpoints

Secondary endpoints are

1. Stable disease (SD) rate
2. Duration of response (DoR)
3. Time to progression (TTP)
4. Progression-free survival (PFS)
5. Incidence and severity of AEs

Statistical Analysis Plan Final Version 4.0

6. Number and proportion of patients who potentially develop anti-MOR00208 antibodies and semiquantitative (anti-MOR00208 antibody titer determination of confirmed positive samples) anti-MOR00208 antibody assessments
7. Pharmacokinetics (C_{max} , t_{max} , C_{pd} [apparent trough serum concentration before dosing], AUC_{0-t} , λ_z , $t_{1/2}$)
8. Absolute and percentage change from baseline in measurements of B-, T- and NK cell populations
9. Evaluation of AEs and ORR stratified by Fc γ RIIIa and Fc γ RIIa polymorphism
10. ORR based on central read

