11.1 Adverse Events

The primary safety endpoint is the incidence and severity of adverse events (AEs). This endpoint will be determined based on the Safety Population. If not specified otherwise, the adverse events summary and overall table will be displayed overall, by each NHL subtype, and for the combined group of FL and other indolent NHL.

All adverse events (AEs) and serious adverse events (SAEs) will be coded using the Medical Dictionary for Regulatory Activities (MedDRA), Version 20.1.

Treatment emergent AEs are defined as AEs occurring or worsening after the start (date and time) of the first study treatment and up to 30 days after the last study treatment including all treatment cycles (treatment emergent period). However, adverse events occurring or worsening later than 30 days after the last treatment are defined as treatment emergent if these are considered to be related to the study drug.

If the start date and time of an AE are partially or completely missing, the AE will be assumed to be treatment-emergent if it cannot be definitely shown that the AE did not occur or worsen

during the treatment emergent period (worst case approach). Missing dates and times will not be replaced.

Thus, the following approach will be taken:

- If the start time of an AE is missing but the start date is complete, an AE will only be excluded from treatment emergent AEs if start day is before day of first treatment or start day is after end day of treatment emergent period.
- If start time and day are missing but the start month is complete, an AE will only be excluded from treatment emergent AEs if start month is before month of first treatment or start month is after end month of treatment emergent period or if stop date/time is before start of first treatment.
- If start day and months are missing but the start year is complete, an AE will only be excluded from treatment emergent AEs if start year is before year of first treatment or if start year is after end year of treatment emergent period or if stop date/time is before start of first treatment.
- If start date is completely missing, an AE will not be excluded from treatment-emergent AEs unless the stop date/time is before start of first treatment.

Time from first treatment to onset of AE [days] will be calculated for complete dates only and will be included in listings.

An AE summary table will be presented showing the incidence and frequency of any

- Treatment-emergent AEs (TEAEs)

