- Serious Adverse Events (SAEs)
- Serious Adverse Events (SAEs) related to MOR00208
- MOR00208-related TEAEs
- MOR00208-related TEAEs by toxicity (according to NCI-CTC toxicity criteria)
- MOR00208-related TEAEs by severity
- Infusion related TEAEs
- TEAEs leading to any action on MOR00208
- TEAEs leading to discontinuation of MOR00208
- TEAEs leading to death

Statistical Analysis Plan Final Version 4.0

The incidence refers to the number and percentage of patient with at least one TEAE of the specified type and the frequency to the number of AEs.

The analyses by toxicity will be based on the NCI-CTC grade (per National Cancer Institute Common Toxicity Criteria, version 4.0). If the NCI-CTC grade is not available, this will be analyzed as “Missing”.

Summaries of incidence rates (number and percentage of patients) and frequencies (number of AEs) of individual TEAEs by MedDRA System Organ Class (SOC) and Preferred Term will be prepared overall and by NHL subtype. Such summaries will be displayed for all

- TEAEs
- TEAEs by toxicity according NCT-CTC
- TEAEs by severity
- TEAEs suspected to be related to MOR00208
- TEAEs leading to discontinuation of MOR00208
- Infusion related TEAEs
- Cytokine release syndromes
- Treatment-Emergent Serious Adverse Events
- TEAEs suspected to be related to MOR00208
- Serious Adverse Events suspected to be related to MOR00208 (Serious Adverse Reactions)
- TEAEs of toxicity grade 3 or higher
- MOR00208-related TEAEs of toxicity grade 3 or higher
- TEAEs of special interest (ie, infusion-related reactions of grade 3 or higher, cytokine release syndrome, allergic reaction to MOR00208 of grade 3 or higher and overdoses)
- Haematological Treatment Emergent Adverse Events
- Overdoses (defined as exceeding planned dose by more than 10%)
- Death cases (irrespective of death due to progressive disease or other reason)
- Pre-treatment AEs (based on all Screened Patients instead of the Safety Population)

A summary of all TEAEs will also be provided by FcγR polymorphisms.

In these summaries each patient will be counted only once within each preferred term to calculate the incidences.

AE listings of all adverse events with the following details will be provided for

- AEs – details
- AEs – action taken
- AEs – coding details

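### TEAE comparisons by FcγR genotype and NHL subtype use crude percentages and counts over a treatment-emergent period whose length depends on response

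*SAP*

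**What the plan says.** SAP section 2.2.2 lists as secondary endpoint 9 "Evaluation of AEs and ORR stratified by" FcγRIIIa and FcγRIIa polymorphism. SAP section 11.1 carries out the AE part: "A summary of all TEAEs will also be provided by FcγR polymorphisms". The same section plans "Summaries of incidence rates (number and percentage of patients) and frequencies (number of AEs) of individual TEAEs" overall and by NHL subtype.

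The measure is crude: "The incidence refers to the number and percentage of patient with at least one TEAE of the specified type", with the number of AEs alongside.

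The period runs from the first treatment "up to 30 days after the last study treatment including all treatment cycles (treatment emergent period"). It has an open-ended extension for events attributed to MOR00208: "adverse events occurring or worsening later than 30 days after the last treatment are defined as treatment emergent if these are considered to be related".

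Treatment length follows response. The Protocol (synopsis and section 10.2) gives eight infusions in two cycles to all, and a third cycle to patients with at least SD on Cycle 2 Day 28. Section 7.1 adds: "Patients with an ongoing response of at least PR at the end of Cycle 3 (regardless of Stage 1 or 2) may receive further study" medication. Such treatment lasts until progression, and who receives it is decided case by case by investigator and sponsor. Section 10.4 foresees dosing beyond four years, with AEs still entering the study database.

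Neither document plans an exposure-adjusted AE rate, a common-window AE table, or a split of AEs into main and maintenance phases. Time to AE onset appears in listings only. Duration of exposure is summarised (SAP sections 7.3.5 and 11.6) but is not linked to AE incidence.

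**The concern.** A crude percentage compares groups fairly only if patients are observed for similar lengths of time. Here observation time is partly a result of response, and the SAP analyses ORR by the same genotypes and subtypes. If one genotype responds more often, more of its patients go on to maintenance and are watched for longer. The TEAE table then mixes toxicity with time at risk, and a larger sample would not separate the two.

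At stake is the reading of a named secondary endpoint, and of any comparison of AE rates between subtypes. A difference could appear where toxicity per unit time is equal, or a real one could be hidden. The primary endpoint is not touched.

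**Working it through.** The documents state no TEAE rate or window length, so there is no figure of the plan to reproduce on this point.

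**Windows, from the dosing schedule (last infusion day − 1 + 30)**
- Two cycles: Cycle 2 Day 22 is study day 28 + 22 = 50. Window 50 − 1 + 30 = 79 days.
- Three cycles: Cycle 3 starts two weeks after Cycle 2 Day 22, on day 64, and its last infusion is on day 85. Window 85 − 1 + 30 = 114 days.
- With maintenance added: 479 days at one year, 845 at two, 1,575 at four. These are about 6, 11 and 20 times the 79 days.

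SAP section 8.1 describes entry to Cycle 3 as PR or CR only, which conflicts with at least SD in SAP section 3.1 and the Protocol. The passages need reconciling; the at-least-SD wording is used here.

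**Model.** Every patient has the same constant hazard h per month, so there is no group effect on toxicity. The risk over t months is P(t) = 1 − exp(−h·t). Days are divided by 30.4375 (SAP section 7.1): 79 days = 2.60 months, 114 days = 3.75 months. Assumed, because the documents give no such figures: h = 2%, 3% or 5% per month; ORR 40% against 20%; 12 or 24 months at risk in responders on maintenance.

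A group's crude risk is ORR × P(responder) + (1 − ORR) × P(non-responder). The difference between groups is therefore 0.20 × [P(responder) − P(non-responder)].

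**Case A: all responders on maintenance, all non-responders at 79 days**

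| h per month | P(79 d) | P(12 m) | P(24 m) | Difference, 12 m | Difference, 24 m |
|---|---|---|---|---|---|
| 2% | 5.1% | 21.3% | 38.1% | 3.3 points | 6.6 points |
| 3% | 7.5% | 30.2% | 51.3% | 4.5 points | 8.8 points |
| 5% | 12.2% | 45.1% | 69.9% | 6.6 points | 11.5 points |

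At 3% the group percentages are 16.6% against 12.0% (12 months) and 25.0% against 16.3% (24 months).

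**Case B: half of responders on maintenance and the other half at 114 days; non-responders split evenly between 79 and 114 days**

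| h per month | Non-responders | Responders, 12 m | Responders, 24 m | Difference, 12 m | Difference, 24 m |
|---|---|---|---|---|---|
| 2% | 6.1% | 14.3% | 22.7% | 1.6 points | 3.3 points |
| 3% | 9.1% | 20.4% | 31.0% | 2.3 points | 4.4 points |
| 5% | 14.6% | 31.1% | 43.5% | 3.3 points | 5.8 points |

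**Common window.** If everyone is observed for the same time, the model gives a difference of zero. This is a property of the model. A real table falls short of it where patients stop early: Protocol section 11.1 records unrelated AEs only to 30 days after the last dose, so a patient who stops after one infusion is covered for about 30 days, against 56 for one followed to Cycle 2 Day 28.

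**Precision.** At 16.6% against 12.0% with 30 patients per group, the 95% half-width of the difference is 1.96 × √[(0.166 × 0.834 + 0.120 × 0.880)/30] = 0.177, about 18 points. With 50 per group it is about 14 points.

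**The case against.** A reader might infer that observation lasts weeks in non-responders and years in responders, so that groups that respond better will look more toxic. The documents do not support that reading:

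- Patients with SD qualify for a third cycle. Maintenance needs an ongoing PR or better at the end of Cycle 3, is worded as optional, and is decided case by case. A responder by best response may never receive it.
- The direction is a tendency. In the Phase I study all infusion reactions fell in the first infusion (Protocol section 4.2.2), and such rows barely change with window length. A higher AE hazard in progressing patients would work the other way.
- The phrase about all treatment cycles in SAP section 11.1 does not name maintenance. If it meant Cycles 1–3 only, the gap would shrink to 114 against 79 days: at most 0.20 × (17.1% − 12.2%) = 1.0 point at 5% per month. SAP section 7.3.5 counts maintenance towards the date of last study treatment, which favours the wider reading.

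The case for leaving the plan alone is that nothing is tested (Protocol section 14.10), genotyping is optional (section 10.9.7), no decision rule uses these tables, and sampling error exceeds the artefact in every scenario above. Exposure duration and the number entering maintenance are already summarised, and laboratory toxicity grades are tabulated by time point.

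These points limit the weight of the concern but do not remove it. The distortion is systematic, it bears on the comparison that the endpoint was listed to make, and separate exposure tables do not let a reader correct an AE percentage.

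**Conclusion.** The concern holds in a limited form. SAP section 11.1 compares genotypes and subtypes over treatment-emergent periods that depend on response. If response differs between groups, later or slowly accruing TEAEs and AE counts will tend to look more frequent in the better-responding group at equal toxicity per unit time.

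Under the stated assumptions the artefact is about 3–12 points if all responders get maintenance, and about 1.6–5.8 points in the milder case. Both ranges rest on assumed hazards, ORRs, maintenance uptake and durations; the true size is unknown, and the subtype tables are not quantified separately. The effect is on the interpretation of descriptive tables in small groups. It is a worthwhile, cheap improvement and does not invalidate the safety analysis.

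**What to change.** In SAP section 11.1:

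1. Add the FcγR-genotype and NHL-subtype TEAE summaries restricted to onset from first dose through Cycle 2 Day 28, the stretch in which all patients have the same eight planned infusions.
2. Name these as the tables used for comparison between groups.
3. Show with them, for each group, the number of patients who stopped before Cycle 2 Day 22, because their observation can end earlier.
4. Keep the whole-period tables, and present the planned duration of exposure by group beside them.

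A separate maintenance-phase table is optional and is more than an onset filter. SAP section 7.3.5 says that administration details are captured only for Cycles 1–3 and that the date of last study treatment is approximated for patients in maintenance. The same gap weakens rates per patient-year.

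The cost is a repeat of existing tables with an onset filter, since time from first treatment to AE onset is already derived where dates are complete; a rule for partial dates is needed. The downside is extra output and fewer events in the short window. Late toxicity remains visible in the whole-period tables.

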11.2 Clinical Laboratory Evaluations

Safety monitoring for all patients enrolled in the study will include among others laboratory assessments: hematology, blood chemistry, and urinalysis, coagulation, and anti-MOR00208 antibodies. Hematology, serum chemistry, immunoglobulins, coagulation, urinalysis will be analyzed by the respective local laboratories of each involved site. Immunogenicity of MOR208 will be estimated by a central laboratory (please refer to section 11.7 for details).

The analysis of laboratory parameters will be presented separated into blood parameters (hematology, serum chemistry, immunoglobulin, coagulation) and urine parameters

(urinalysis). All data will be listed.

The blood parameters will be transformed to SI values based on SI units to make laboratory parameters comparable between different local laboratories. The relevant reference ranges supplied by each laboratory will also be transformed to SI reference ranges for each laboratory. The SI reference ranges will be presented in the listings.

Descriptive summaries of absolute values and changes from baseline will be presented for all blood parameters.

Each abnormal value will be flagged to show whether it is a value below or above the reference range. For the assessment of laboratory variables, 5 categories will be used that take into account the investigator's assessment of clinical relevance: 'clin. sign., above', 'non-clin. sign., above', 'within', 'non clin. sign., below', 'clin. sign., below'.

The assessment of laboratory variables will be tabulated by time point for each clinical laboratory analyte (frequency tables).

Additionally, for each laboratory parameter, shifts in assessments from baseline to all post administration time points will be presented.

If NCI-CTC grades are available for a clinical laboratory analyte, these will be derived according to Common Terminology Criteria for Adverse Events version 4.0 (CTCAE) and used to present additional frequency and shift tables based on NCI-CTC grades.

The investigator's assessment of categorical urinalysis variables ('normal', 'abnormal, not clin. sign.', 'abnormal clin.sign.') will be tabulated by time point for each urine parameter (frequency tables).

Additionally, for each of these urine parameter shifts in assessments from baseline to all post-administration time points will be presented.

Laboratory values that are outside the reference range will also be flagged in the data listings, along with corresponding reference ranges.

Results of urine microscopy (if available), results of the pregnancy test and screening serology results will only be included in listings.

11.3 Vital Signs and Body Weight

Descriptive summaries of actual values and changes from baseline will be calculated for vital signs (Systolic Blood Pressure, Diastolic Blood Pressure, Body Temperature, Heart Rate and

Respiratory Rate) and Body Weight and BMI. These summaries will be presented for all time points.

Each abnormal value will be flagged to show whether it is a value below or above the normal limit. The normal limits are detailed in the appendix of the study protocol (Section 17.2 of the study protocol).

11.4 Electrocardiograms

The summary ECG assessment (categories: <normal; abnormal clinically significant; abnormal not clinically significant>) will be tabulated by visit.

Each abnormal PR, QRS, and RR interval value will be flagged to show whether it is a value below or above the normal limit. The normal limits are detailed in the appendix of the study protocol (Section 17.2 of the study protocol).

Descriptive summaries of actual values and changes from baseline will be presented by visit for ECG measures of RR interval, PR interval, QRS interval, QT interval, QTc interval (both correction methods), and HR (Heart rate).

The Bazett's Correction (QTc_b) and Fridericia's Correction (QTc_f) for the QTc interval will be derived as follows:

$$\text{Bazett's Correction (QTc}_b\text{)} \quad QTc_b = \frac{QT_{msec}}{\sqrt{RR}}$$

$$\text{Fridericia's Correction (QTc}_f\text{)} \quad QTc_f = \frac{QT_{msec}}{\sqrt[3]{RR}}$$

where: Relative Rate: $RR = 60 / HR$

HR = Heart Rate obtained from the ECG.

Also, the number and percent of patients with QTc values (for both corrections) above the normal limit (451-480 ms, 481-500 ms, or > 500 ms) and the number and percent of patients who experienced a change > 30 ms or a change > 60 ms from baseline will be presented by visit.

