14.7.5 Electrocardiograms

Electrocardiogram data will be summarized as change from baseline. The summary ECG assessment (categories: "normal; abnormal clinically significant"; "abnormal not clinically significant") will be tabulated by time point for the Safety Population.

Each abnormal PR (ECG), QRS, and RR interval value will be flagged to show whether it is a value below or above the normal limit. The normal limits are detailed in the appendix ([Section 17.2](#)).

Summary statistics for all time points will be displayed for QT and both QTc correction methods, side-by-side. The Bazett's corrections method for QTc will be applied as follows:

$$\text{Bazett's Correction (QTc}_b\text{)} \quad \text{QTc}_b = \frac{QT_{msec}}{\sqrt{RR}}$$

where: Relative Rate: RR = 60/HR

Also, the number and percentage of patients with QTc values above the normal limit (441-480 ms, 481-500 ms, or > 500 ms) and the number and percentage of patients who experienced a change > 30 ms or a change > 60 ms will be presented by time point.

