17.2 Normal Limits for Vital Signs, Weight, Height, and Electrocardiogram Intervals

Table 5 Criteria For Normal Limits For Vital Signs, Height, And Weight

Body Weight, Body Height, Vital Signs Parameter	Normal Limits	
	Low	High
Systolic BP (mm Hg)	85	139
Diastolic BP (mm Hg)	60	89
Heart rate (bpm)	60	100
Respiration rate (rpm)	12	22
Body temperature (°C)	36.4°C	37.7°C
Oxygen saturation (%)	93	100
Body weight (kg) ^a	41	113
Body mass index (kg/m ²) ^b	18.5	24.9

^a Changes in body weight are evaluated by the investigator (without taking height into account), because body mass index is not collected on the electronic case report form.

^b Body mass index is calculated and analyzed retrospectively by the sponsor, at which time height is taken into account.

Table 6 Criteria For Normal Limits For Electrocardiograms

ECG Variable	Normal Limits (msec)	
	Low	High
PR interval	120	200
QRS interval	50	100
RR interval	600	1000
QT interval (gender not specified)	-	≤440
QTc interval ^a (gender not specified)	-	≤440

^a No lower boundary will be set for QTc.

Product Name: MOR00208
Date: 26 May 2020
Protocol Amendment 5, Final v7.0

Protocol Number: MOR208C201
IND Number: 114,856
EudraCT Number: 2012-002659-41

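### SAP 11.4 counts QTc above normal only from 451 ms, whereas the protocol counts from 441 ms against a limit of 440 ms, so values of 441 to 450 ms fall in no QTc outlier band

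*SAP*

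**What the plan says.** Three places bear on the point.

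- **SAP 11.4 (Electrocardiograms)** plans the number and percent of patients, by visit and for both the Bazett and Fridericia corrections, with QTc "above the normal limit (451-480 ms, 481-500 ms, or > 500 ms".
- **Protocol 14.7.5 (Electrocardiograms)** plans the same count for patients "with QTc values above the normal limit (441-480 ms, 481-500 ms, or > 500 ms".
- **Protocol 17.2, Table 6** gives the limit itself: "QTc interval ^a (gender not specified) - ≤440" (in msec; no lower boundary is set).

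The SAP states no QTc limit of its own. The one source it names for ECG limits is the protocol appendix: "The normal limits are detailed in the appendix of the study protocol (Section 17.2 of the study protocol". That reference directly follows the flagging rule, which covers other intervals only: "Each abnormal PR, QRS, and RR interval value will be flagged to show whether it is a value below or above the normal limit". SAP Section 12 lists three changes from the protocol: the PK population, ORR by central read, and dropping the CD19 stratification. The QTc bands are not among them.

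**The concern.** The two documents describe the same table in nearly the same words, and their upper bands agree. Only the lower edge of the first band differs, by 10 ms. In the protocol that edge follows from Table 6. In the SAP it follows from nothing stated. A programmer working from the SAP would produce a table described as showing patients above the normal limit that leaves out some patients who are above it.

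The study has a single arm, so the absolute count at each visit is the result. There is no control group in which the same omission would also occur. SAP 11.4 does not flag individual QTc values against a limit, so no other threshold-based QTc output recovers the missing patients.

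**Working it through.** **Inputs**

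| Item | Value | Source |
|---|---|---|
| QTc upper normal limit | 440 ms | Protocol 17.2, Table 6 |
| Protocol bands | 441-480, 481-500, > 500 ms | Protocol 14.7.5 |
| SAP bands | 451-480, 481-500, > 500 ms | SAP 11.4 |
| Change criteria | > 30 ms, > 60 ms | both documents |

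**Step 1. Reproduce the lower edge.** QTc is taken in whole milliseconds, as the printed bands imply. A limit of 440 ms or less makes the first value above it 440 + 1 = 441 ms. That reproduces the protocol's edge but not the SAP's edge of 451 ms.

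**Step 2. Check coverage.** Each whole-millisecond value above 440 ms was tested for membership in a band.

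- Protocol bands: every value falls in exactly one band; none is left out.
- SAP bands: 441, 442, ..., 450 fall in none, which is 450 − 441 + 1 = 10 values.
- Width of the first band: protocol 480 − 441 + 1 = 40 values; SAP 480 − 451 + 1 = 30 values.

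**Step 3. See what else captures these values.** SAP 11.4 also says: "Descriptive summaries of actual values and changes from baseline will be presented by visit for ECG measures", and QTc by both corrections is among those measures. The change counts can catch some patients. A reading of 445 ms counts as a change of more than 30 ms if baseline was below 445 − 30 = 415 ms, and as more than 60 ms if baseline was below 445 − 60 = 385 ms. A patient at 445 ms with a baseline of 430 ms is in neither change count and in no outlier band.

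**Step 4. Illustrate the size.** The documents give no QTc mean or SD, so this step is assumption only. For a normal QTc with mean m and SD s:

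- share above 440 ms: A = 1 − Φ((440.5 − m)/s)
- share in the gap: G = Φ((450.5 − m)/s) − Φ((440.5 − m)/s)

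For example, with m = 410 and s = 20, A = 1 − Φ(1.525) = 0.0636 and G = Φ(2.025) − Φ(1.525) = 0.0422.

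| m (ms) | s (ms) | A | G | G/A |
|---|---|---|---|---|
| 400 | 20 | 2.1% | 1.6% | 73% |
| 400 | 25 | 5.3% | 3.1% | 59% |
| 410 | 20 | 6.4% | 4.2% | 66% |
| 410 | 25 | 11.1% | 5.9% | 53% |
| 420 | 20 | 15.3% | 8.9% | 58% |
| 420 | 25 | 20.6% | 9.5% | 46% |

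These are shares of readings, whereas the SAP counts patients by visit. One distribution is used for both corrections, although Bazett and Fridericia values differ unless heart rate is 60.

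**The case against.** A reader might infer that values of 441 to 450 ms are counted nowhere. The documents do not support that. The values enter the by-visit descriptive summaries for both corrections and the individual data listings. The investigator's overall ECG assessment (normal, abnormal clinically significant, abnormal not clinically significant) is tabulated whatever the bands. Some patients will meet a change criterion. Protocol 10.8.5 also asks for new, clinically significant ECG abnormalities to be reported as AEs. What is lost is the outlier count only.

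A reader might also infer that the SAP expressly adopts 440 ms for QTc. It does not. Its reference to protocol 17.2 follows the sentence on PR, QRS and RR, and the later QTc sentence prints its own bands without repeating the reference. Applying Table 6 to QTc is an inference, though a strong one, because neither document gives another QTc limit. Printing the bands would let a careful reader see that the lowest starts at 451 ms, but it would not tell that reader that the limit is 440 ms.

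A third inference is that the SAP made an undeclared change to its protocol. That cannot be settled here. The SAP is dated 3 April 2019 and was written to protocol Amendment 4, version 6.0. The protocol available is Amendment 5, version 7.0, of 26 May 2020. The version 6.0 wording cannot be seen, and protocol 14.13 also allows deviations to be described in the study report. This caveat limits only the point about declaration. The later protocol still has 441 ms and 440 ms, so the two documents as they stand disagree.

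Finally, the percentages follow from an assumed distribution and are not evidence about this trial. That objection stands in full. The consequence is also small: QTc is not a named endpoint, there is no inferential testing, and the bands above 480 ms agree between the documents.

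**Conclusion.** The SAP's bands are wrong as written against the only QTc limit that the documents state. At each visit, the count of patients above normal is understated by the number whose QTc is 441 to 450 ms. If no patient has such a value, the count is unchanged. The gap of ten whole-millisecond values is certain. How many patients fall in it is unknown. Under the assumed range (normal, mean 400-420 ms, SD 20-25 ms) about 1.6% to 9.5% of readings would do so, and this should be read as illustration only.

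This is a minor defect in one descriptive safety table. Counts above 480 ms and the change-from-baseline counts are unaffected, and so are all efficacy and futility results. No stopping criterion in protocol 9.12 and no pre-dose limit in protocol Table 4 uses QTc.

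**What to change.** Amend the QTc sentence in SAP 11.4, for both corrections, in one of these ways:

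1. Start the first band at 441 ms, giving 441-480, 481-500 and > 500 ms as in protocol 14.7.5.
2. Add a 441-450 ms band ahead of 451-480 ms. This keeps the SAP's existing counts visible and still accounts for every value above 440 ms.
3. If a 450 ms limit was intended, state it, relabel the table so that it no longer implies the Table 6 limit, and declare the change with its reason in SAP Section 12.

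Any of the three resolves the contradiction. The cost is one SAP line and the matching table shell, plus a rerun of that table if it has already been produced. Under options 1 and 2 the total above normal can only stay the same or rise.
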